**Table 5 Best Overall Response When Confirmation of CR/PR Is Required**

Overall response 1st time point	Overall response subsequent time point	Best overall response (BOR)
CR	CR	CR
CR	PR	SD, PD or PR a
CR	SD	SD provided minimum criteria for SD duration met; otherwise, PD
CR	PD	SD provided minimum criteria for SD duration met; otherwise, PD
CR	NE	SD provided minimum criteria for SD duration met, otherwise NE
PR	CR	PR
PR	PR	PR
PR	SD	SD

Overall response 1st time point	Overall response subsequent time point	Best overall response (BOR)
PR	PD	SD provided minimum criteria for SD duration met, otherwise, PD
PR	NE	SD provided minimum criteria for SD duration met, otherwise NE
NE	NE	NE

CR = complete response, PR = partial response, SD = stable disease, PD = progressive disease, NE = in-evaluable.

a If a CR is truly met at first time point, then any disease seen at a subsequent time point, even disease meeting PR criteria relative to baseline, makes the disease PD at that point (since disease must have reappeared after CR). Best response would depend on whether minimum duration for SD was met. However, sometimes 'CR' may be claimed when subsequent scans suggest small lesions were likely still present and in fact the subject had PR, not CR at the first time point. Under these circumstances, the original CR should be changed to PR and the best response is PR.

The confirmed ORR by treatment group will be calculated along with the two-sided 95% CI using the Clopper-Pearson method (exact CI for a binomial proportion as computed by default by the FREQ procedure using the EXACT option).

The association of treatment effect and ORR will be tested by the General Association Statistic of the Cochran-Mantel-Haenszel test (CMH) with the stratum of region taken into account. The null hypothesis of no association in any region is tested against the alternative, which specifies that there is an association between treatment effect and ORR in any given region. The CMH test will be performed with one-sided alpha level of 0.025 at the primary analysis only.

In case the assumptions of the CMH test are violated due to a small number of subjects in some strata (i.e., number of subjects  $\leq 10$  in at least one of the stratum within each treatment arm), a Fisher's exact test will be used.

The stratified odds ratio in terms of objective response (OR) will also be estimated with a Mantel-Haenszel estimator along with its 95% CI to compare the treatment effect. The odds ratio is defined as the odds of OR with avelumab divided by the odds of OR with chemotherapy. The Breslow-Day test will be used to test the null hypothesis that odds ratios in all regions are equal against the alternative hypothesis that the odds ratio in at least one region is different.

In case the null hypothesis of homogeneity of odds ratios across regions is not rejected at the alpha level of 5% two-sided, the common odds ratio will be determined as the Mantel-Haenszel estimate (by the SAS FREQ procedure using the CMH option); if the null hypothesis of homogeneity of odds ratios across all regions is rejected, the odds ratio per region will be calculated with the corresponding exact CI.

In addition, the frequency (number and percentage) of subjects with BOR of CR, PR, SD, PD, non-CR/non-PD (applicable only to subjects with non-measurable target-lesion disease at screening), and NE will be tabulated. Patients with BOR of NE will be summarized by reason for having NE status. The following reasons will be used:

---

[REDACTED]

- No post-baseline assessments
- All post-baseline assessments have overall response NE
- No post-baseline assessments due to death within 6 weeks after randomization
- No post-baseline assessments due to other reasons
- New anticancer therapy started before first post-baseline assessment
- SD of insufficient duration (< 6 weeks after date of randomization without further evaluable tumor assessment)
- PD too late (i.e. tumor assessment of PD was >12 weeks after date of randomization and there was no tumor assessment in between)
- NED maintained post Re-Baseline

Special and rare cases where BOR is NE due to both early SD and late PD will be classified as ‘SD too early’.

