4.2 Secondary Objectives

Secondary objectives are as follows:

- To demonstrate superiority of maintenance therapy with avelumab versus continuation of first-line chemotherapy with regard to PFS as per RECIST v1.1 according to Investigator assessment.
- To demonstrate superiority of maintenance therapy with avelumab versus continuation of first-line chemotherapy with regard to the ORR as per RECIST v1.1 and per Investigator assessment
- To compare the subject-reported outcomes / quality of life (QoL) of subjects when treated with avelumab versus continuation of first-line chemotherapy as assessed by the European QoL 5-dimensions 5 Level Questionnaire (EQ-5D-5L), and the European Organization for Research and Treatment of Cancer (EORTC) QLQ-C30 and module QLQ-STO22
- To determine the safety and tolerability of avelumab.

5 Investigational Plan

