8.5.3.2 Key Secondary Endpoint – Best Overall Response

For the analysis of BOR in the Maintenance Phase (see Section 8.5.3) according to RECIST v1.1 and per Investigator assessment, the ORR (defined as having a confirmed BOR of CR or PR) will be calculated along with corresponding 2-sided exact Clopper-Pearson 95% CIs for the two treatment arms. The Cochran-Mantel-Haenszel test will be stratified by region (Asia versus non-Asia) to compare the ORR between the two treatment arms. In case the assumptions of the Cochran-Mantel-Haenszel test are violated due to a small number of subjects in some strata, a Fisher's exact test will be used. This analysis will be based on the ITT Analysis Set.

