## 5 Summary of Clinical Trial Features

Trial objectives	
Primary objectives: The primary objectives are to demonstrate superiority of maintenance therapy with avelumab versus continuation of first-line chemotherapy with regard to Overall Survival (OS) in all randomized subjects or in PD-L1+ subjects who have not progressed on first-line chemotherapy.
 
Secondary objectives:
 

• To demonstrate superiority of maintenance therapy with avelumab versus continuation of first-line chemotherapy with regard to Progression-Free Survival (PFS) as per Response Evaluation Criteria in Solid Tumors version 1.1 (RECIST v1.1) and per Investigator assessment.

• To demonstrate superiority of maintenance therapy with avelumab versus continuation of first-line chemotherapy with regard to objective response rate (ORR) as per RECIST v1.1 according to investigator assessment.

• To compare the subject-reported outcomes / quality of life (HRQoL) of subjects when treated with avelumab versus continuation of first-line chemotherapy as assessed by the European QoL 5-dimensions 5-levels questionnaire (EQ-5D-5L), and the European Organization for Research and Treatment of Cancer (EORTC) QLQ-C30 and module QLQ-STO22

• To determine the safety and tolerability of avelumab

-------------------------	---

CCI

	

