### Subgroup Analysis Set

Subgroup analyses will be performed on primary and key secondary efficacy endpoints based on the subgroups as defined below.

In order to include baseline variables in the Cox proportional hazards model for OS and PFS multivariate analysis, and the logistic model for BOR multivariate analysis, indicator variables will be defined for each subgroup category except for the reference category, against which all other categories are compared. In case a low number of subjects (i.e. < 5% of the randomized population) is observed in a given subgroup category, categories may be pooled. Subgroup analyses will not be performed on or include any subjects with missing values for a given subgroup.

In addition, primary and key secondary endpoint tables will be repeated for the group of subjects who are treated in Japan. Japan-specific outputs will follow the format of the overall primary/secondary end-point tables and will display one-sided p-values. These tables will omit the geographically-stratified analysis.

The parameterization used for the primary analysis will be updated and finalized at the Data Review Meeting, at the latest, and documented in an amendment to this SAP, should it differ from the following definitions.

The subgroups are as follows:

- PD-L1 Assay Status – Tumor cells
    - < 1% (Reference)
    - $\geq 1\%$
  - Age Group 1
    - Age at randomization < 65 years (Reference)
    - Age at randomization  $\geq 65$  years
  - Age Group 2
    - Age at randomization < 75 years (Reference)
    - Age at randomization  $\geq 75$  years
  - Gender
    - Male (Reference)
    - Female
  - Race
    - Caucasian / White (Reference)
    - Asian
-

- Black/ African American
  - Other
  - Pooled Geographical Region:
    - Asia
    - Non-Asia (Reference)
  - ECOG PS at Maintenance Phase baseline
    - ECOG PS 0
    - ECOG PS 1 (Reference)
  - Site of primary tumor
    - Stomach
    - Gastro-esophageal Junction (GEJ) (Reference)
  - Regimen of induction chemotherapy
    - Oxaliplatin + 5-FU (Reference)
    - Oxaliplatin + Capecitabine
  - Re-Baseline Response per Independent Radiologist
    - CR, PR (Reference)
    - SD, non-CR/non-PD
  - Microsatellite Instability Biomarker Status
    - Stable (Reference)
    - High
  - Presence of Liver Metastasis
    - Diagnosis of metastatic liver
    - No diagnosis of metastatic liver (reference)
  - Presence of Peritoneal Carcinomatosis
    - Diagnosis of peritoneal carcinomatosis

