### Significance level:

The overall significance level is 2.5%, one-sided. The confirmatory statistical tests for the primary and key secondary efficacy endpoint analyses are described in Sections 15.1 and 15.2. Section 7 describes the procedures for controlling the overall type I error rate in the study. The statistical tests to compare treatment arms on other secondary, CCI [REDACTED], and safety analyses CCI [REDACTED] [REDACTED]

Confidence intervals will be two-sided with a confidence probability of 95%, unless otherwise specified.

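### Does the confirmatory ORR test lack a rule for turning an unsigned CMH chi-square into a one-sided decision?

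*SAP*

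**What the plan says.** **The test.** SAP 15.2.2 says that the association between treatment and ORR "will be tested by the General Association Statistic of the Cochran-Mantel-Haenszel test (CMH"), stratified by region. The null is no association in any region. The alternative is that "there is an association between treatment effect and ORR in any given region". The level follows: "The CMH test will be performed with one-sided alpha level of 0.025 at the primary analysis only". If strata are too small, Fisher's exact test replaces CMH, and its side is not given. Protocol 8.5.3.2 says only that the stratified CMH test serves "to compare the ORR between the two treatment arms".

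**The objective.** SAP 5 reads "To demonstrate superiority of maintenance therapy with avelumab versus continuation of first-line chemotherapy with regard to objective response rate (ORR"), and Protocol 4.2 reads "To demonstrate superiority of maintenance therapy with avelumab versus continuation of first-line chemotherapy with regard to the ORR".

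**The level.** SAP 10, under Significance level, says "The overall significance level is 2.5%, one-sided". Protocol 8.5.1 and the text after Table 3 in SAP 15 both allot best overall response (BOR) the full 2.5% one-sided error, once PFS has been rejected.

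**Related wording.** SAP 15.2.2 orients the odds ratio as avelumab over chemotherapy. Its subgroup paragraph expressly calls the CMH test for subgroup levels two-sided. SAP 9 says of the Japan tables: "Japan-specific outputs will follow the format of the overall primary/secondary end-point tables and will display one-sided p-values".

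**The concern.** The ORR paragraph puts together three things that do not fit on their face: a statistic with no sign, an alternative with no direction, and a one-sided level. SAP 15.1 gives OS a directional alternative and a one-sided log-rank test, and SAP 15.2.1 makes PFS analogous. ORR is therefore the only confirmatory step worded without a direction.

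A programmer who takes the general association p-value and compares it with 0.025 would run the test at half its allotted level towards avelumab. The same data could then pass or fail depending on how one paragraph is read. A confirmatory rule should not be open to that choice once the p-value is known.

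**Working it through.** **Is there a planning figure to reproduce?** Not for ORR: the documents give no assumed response rates and no power. The one-sided convention can be checked on OS. With Lan-DeMets O'Brien-Fleming spending at one-sided 0.02 and information fraction 0.75, the interim level is 0.0072 (z = 2.446). The final level is 0.0178 (z = 2.101), or 0.0233 (z = 1.990) after recycling. Power at 356 events and HR 0.70 is 0.9007. All agree with Protocol 8.1 and 8.6 and SAP Table 3, so the plan's one-sided levels mean what they say.

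**Three ways to use the chi-square.** For two arms and a binary response, chi-square(1) = Z².

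| Decision rule | Critical value of Z | Null rejection towards avelumab | Total null rejection |
|---|---|---|---|
| p < 0.025, no direction | 2.241 in absolute value (chi-square 5.024) | 0.0125 | 0.025 |
| p < 0.05, no direction | 1.960 in absolute value (chi-square 3.841) | 0.025 | 0.05 |
| p < 0.05 and effect favours avelumab | Z > 1.960 | 0.025 | 0.025 |

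Only the third row is a one-sided test at 0.025. The first is a two-sided test at 0.025 and the second a two-sided test at 0.05. Simulation of the stratified CMH test (499 subjects, 1:1, 400,000 replicates; assumed Asia share 20% or 50%, common ORR 10%, 15% or 20%) gave 0.0121 to 0.0126 towards avelumab for the first row and 0.0248 to 0.0254 for the third.

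**Cost if the first row were used by mistake.** Inputs: 249.5 per arm (499/2; the 499 is in Protocol 8.1) and assumed ORRs. Power = Φ((δ − z·SE0)/SE1), with SE0 from the pooled rate and SE1 from the separate rates. For 10% v 5%:

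- SE0 = √(2 × 0.075 × 0.925/249.5) = 0.02358
- SE1 = √((0.09 + 0.0475)/249.5) = 0.02348
- z = 2.241: (0.05 − 0.05285)/0.02348 = −0.121, power 45.2%
- z = 1.960: (0.05 − 0.04622)/0.02348 = 0.161, power 56.4%

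| Assumed ORR, avelumab v control | Unsigned p < 0.025 | One-sided 0.025 | Loss (points) |
|---|---|---|---|
| 10% v 5% | 45.2% | 56.4% | 11.2 |
| 14% v 7% | 62.2% | 72.4% | 10.2 |
| 18% v 10% | 63.2% | 73.2% | 10.0 |
| 18% v 9% | 76.0% | 83.9% | 7.9 |

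**Worked example on assumed counts.** Responders are 8/60 v 5/60 in one region and 27/190 v 15/189 in the other. Observed minus expected avelumab responders: 1.5 + 5.945 = 7.445. Variance: 2.922 + 9.361 = 12.283. Then z = 7.445/√12.283 = 2.124, chi-square p = 0.0337, and half of it is 0.0168. Halving the p-value and taking the signed root are the same operation.

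**How often the step is reached.** Protocol Appendix III reports 438 scored samples, with less than 15% positive: 0.15 × 438 = 65.7 subjects at most. Assuming the overall event fraction, 65.7 × 356/499 = 46.9 events. At the planned HR of 0.54 and the recycled 2.5% level, 0.616 × √(46.9/4) − 1.960 = 0.15, a power of about 56% for OS in PD-L1+ subjects. If the steps are treated as independent, the losses in the table shrink to about 4 to 6 points (0.56 × 7.9 = 4.4; 0.56 × 11.2 = 6.3). They shrink further because OS in all subjects and PFS must also be rejected.

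**The case for a change.** The strongest case for a change is that this is a confirmatory test and its decision rule is not written out. The alternative as worded contradicts the superiority objective, and two or three SAP sentences would mend it at no cost. The avelumab-over-chemotherapy odds ratio does not settle the matter alone: it is an estimate not tied to the decision, and SAP 15.2.2 replaces the common odds ratio with regional ones if homogeneity is rejected.

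The wording criticism stands, and so does the unstated side of the Fisher fallback. Some of the text that might cover this cannot be seen: SAP 6 and part of the Significance level paragraph are redacted, and the testing-strategy figure is not shown. The visible ORR section nevertheless reads as complete, so the conclusion does not lean on the missing text.

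The step from loose wording to a wrong test does not stand. Setting a two-sided p-value against 0.025 means disregarding the word one-sided in the same paragraph. The authors do separate the two cases, since they label the subgroup CMH test two-sided. Direction needs no common odds ratio: the sign of observed minus expected avelumab responders, summed over regions, is always available from the CMH calculation. The same stated level and direction carry over to Fisher's test.

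**Conclusion.** No change is needed. The ORR alternative is loosely worded and the conversion step is left out, but the stated level, the superiority objective and the hierarchy together leave one consistent rule: half the 1-df p-value, in avelumab's favour, against 0.025. An analyst following the whole plan would apply it, and writing it down would alter no correctly run result.

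The 0.0125 level and the conditional loss of about 8 to 11 points belong to a misapplication, and they rest on assumed response rates and 499 subjects split evenly. Even that error would be conservative: it could not produce a false claim for avelumab, it touches no OS or PFS conclusion, and it arises only after both OS hypotheses and PFS have been rejected.

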### **Sensitivity Analysis**

The following sensitivity analyses of ORR will be performed:

1. The analysis of ORR will be repeated on the PP analysis set if this analysis set includes less than 90% of subjects in the FAS;
2. A multivariable logistic regression analysis will be performed to assess and adjust the treatment effect for relevant baseline factors of potential prognostic impact. The subgroup variables defined in Section 9 “Subgroup Analysis Sets” will be included in the model. A stepwise selection procedure will serve to identify explanatory variables of potential prognostic values additional to the randomization strata which will be included in all models during the selection procedure. The level of significance for an explanatory variable to enter the model is set to 0.15 (p-value of Score test) and the significance level for removing it is set to 0.40 (p-value of Wald test). Once this procedure stops, the factor 'treatment group' will be added to the last selected model in order to evaluate the effect of treatment on BOR when adjusted for the selected explanatory variables. The odd ratios of all selected explanatory variables and of treatment effects will be reported including 2-sided 95% confidence intervals. No interactions will be considered. Post-baseline factors will not be considered for the model.

### **Subgroup Analysis**

For the subgroup analysis of BOR, the association of treatment and BOR will be tested using the two-sided CMH test per subgroup level. The ORR along with the two-sided exact Clopper-Pearson 95% CIs will be calculated for each subgroup.

In addition, to assess the heterogeneity of treatment effect across the subgroup levels for the secondary endpoint of BOR, a logistic regression model will be fitted with BOR as the dependent variable (=1 for subjects with a confirmed BOR of PR or CR; =0 otherwise); subgroup, treatment, and with and without the treatment-by-subgroup interaction as explanatory variables. A p-value for the interaction term (Wald Chi-Square test) will be provided together with the odds ratio and corresponding 95% CI of the interaction model parameter.

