Approximately 466 subjects are planned to be randomly assigned into the Maintenance Phase. The actual number of subjects enrolled in the Induction Phase will be driven by observed induction failure rates and will be such to allow for approximately 466 patients to be randomized in the Maintenance Phase. At the time of this protocol amendment, subject

enrollment in the Maintenance Phase is complete, with 499 subjects randomized into the Maintenance Phase.

Primary endpoint:

The primary endpoint of the trial is:

- OS, defined as the time (in months) from randomization to the date of death, regardless of the actual cause of the subject's death.

Secondary endpoints:

The key secondary endpoints are:

- PFS defined as the time (in months) from randomization to the date of the first documentation of disease progression (per RECIST v1.1 and as evaluated by Investigator) or death due to any cause (whichever occurs first).
- Best Overall Response (BOR) in Maintenance Phase according to RECIST v1.1 and per Investigator assessment.

Other secondary endpoints include subject-reported outcomes / QoL (assessed by the EQ-5D-5L, EORTC QLQ-C30, and EORTC module QLQ-STO22 questionnaires).

Safety endpoints:

Safety endpoints include adverse events (AEs), assessed throughout the trial and evaluated using the National Cancer Institute (NCI) Common Terminology Criteria for Adverse Events (CTCAE) v4.03, physical examinations, clinical laboratory assessments, concomitant medications, vital signs, electrocardiogram (ECG) parameters, and ECOG PS.

Diagnosis and key inclusion and exclusion criteria:

Key inclusion criteria

Male or female subjects aged ≥ 18 years, with an ECOG PS of 0 to 1 at trial entry, with the availability of a recently-obtained (within 6 months) biopsy from a non-irradiated area, formalin-fixed, paraffin-embedded (FFPE) block containing tumor tissue or a minimum of 10 (preferably 25) unstained tumor slides (cut within 1 week) suitable for PD-L1 expression assessment, at least 1 measurable tumor lesion, and with histologically confirmed unresectable, locally advanced or metastatic, adenocarcinoma of the stomach or the GEJ.

Key exclusion criteria

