At the time of release of Protocol Version 6, the PD-L1 assay utilized was an investigational use only (IUO) assay for CCI testing. Because the amended primary endpoint of OS in the PD-L1+ analysis set would require testing by validated assay, validation of the proposed PD-L1 IHC 73-10 pharmDx kit for testing of GC samples at 1% cut-off for tumor cells was initiated in September 2018.

Results of the PD-L1 scoring with validated assay became available in June 2019. From 499 randomized subjects, 438 samples were available for PD-L1 scoring with the validated assay. Less than 15% of the samples were scored as PD-L1 positive, which is considerably less than the previously assumed prevalence during Protocol Versions 1-6. Based on this prevalence, the number of previously projected events (Protocol Version 6) in the PD-L1+ subjects will not be reached. Thus, the condition of meeting the pre-specified number of PD-L1+ events for the Final Analysis data cut-off

has been removed as a trigger for the Final Analysis in the Protocol Version 7. The Final Analysis will be triggered by the events in the ITT population as well as a minimum follow-up time of 18 months for primary analysis which is expected to ensure sufficiently mature data for OS in PD-L1+ subjects. The primary analysis of OS in PD-L1+ subjects will be conducted at the same time as OS in all randomized subjects with substantially reduced power, according to the endpoint definition as in Protocol Version 6.

The sampling for PK and CCI analysis was limited to 2 years from randomization, as further sampling will not add value to pharmacokinetic and CCI evaluation. Therefore, the last sampling point will be at Week 109. This will avoid unnecessary burden to the subjects.

The above-mentioned changes are considered substantial based on the ‘Detailed guidance on the request to the competent authorities for authorization of a clinical trial on a medicinal product for human use, the notification of substantial amendments and the declaration of the end of the trial (CT-1)’.

Protocol Version 7.0 Detailed List of Changes

Changes to the clinical trial protocol text with the exception of minor editorial changes to the clinical trial protocol text are presented in the table below. Additions and amended text are shown in bold. Deletions are marked using strike through.

Comparison with Clinical Trial Protocol Version 6.0, 21 June 2018 (Amendment 5)

Change	Section	Page	Previous Wording	New Wording	Rationale

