#### 15.1.4 Subgroup Analysis of Primary Endpoint

*Analysis sets: FAS, PD-L1+*

Subgroup analyses will be performed on the primary endpoint for all subgroup levels defined in Section 9 “Subgroup Analysis Sets”. CCI

No adjustment for multiplicity will be performed. The two treatment arms will be compared using a two-sided unstratified log rank test for each subgroup level. The unstratified HR of avelumab over chemotherapy/BSC-only and its corresponding 95% CI will be computed at each

---

subgroup level. In the case of a low number of subjects within a category (<5% of the randomized population), the categories may be pooled.

The HR and its corresponding 95% CI, overall and for each subgroup level will be presented in a forest plot.

To assess the heterogeneity of treatment effect on OS across the subgroup levels, two Cox regression models will be fitted for each combination of subgroup/primary endpoint. Both models will use subgroup and treatment arm as explanatory variables; the treatment-by-subgroup interaction will be included in the second.

- Model 1: treatment + subgroup
- Model 2: treatment + subgroup + treatment \* subgroup-variable

A p-value for the interaction test (Likelihood Ratio test) will be provided together with the subgroup HR (analysis subgroup level over reference category), point estimate of the regression parameter, and corresponding 95% CI of the interaction model parameter.

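### The Wald test planned for ORR subgroup interactions fails when a two-level subgroup has an arm with no responders; a likelihood-ratio test on the same two models would not

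*SAP*

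**What the plan says.** The Subgroup Analysis paragraph of SAP Section 15.2.2 fits a logistic model for confirmed response with subgroup and treatment, "with and without the treatment-by-subgroup interaction as explanatory variables". It then specifies: "A p-value for the interaction term (Wald Chi-Square test) will be provided together with the odds ratio", plus a 95% CI for the interaction parameter. The same paragraph gives the ORR with Clopper-Pearson limits and a two-sided CMH test at each subgroup level.

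For the same question on OS, SAP Section 15.1.4 fits two nested Cox models and states: "A p-value for the interaction test (Likelihood Ratio test) will be provided together with the subgroup HR".

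SAP Section 9 lists 15 subgroup factors. Thirteen have two levels; race and number of metastatic sites have four. Its small-number rule is that when a low count, defined as under 5% of those randomized, "is observed in a given subgroup category, categories may be pooled". The rule is optional and depends on category size, not on the number of responders. Section 15.2.2 names no fallback for the interaction model when a cell has no responders.

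**The concern.** A Wald statistic takes its standard error from the fitted interaction model. If one arm of a subgroup level has no responders, the maximum-likelihood log odds ratio for that level is infinite, and the estimated variance grows faster than the square of the estimate. The statistic collapses towards zero. The test is therefore blind when the observed contrast in a level is as one-sided as it can be.

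The table would then print an interaction p near 1 and an unusable odds ratio and CI beside response counts that point the other way. PD-L1 status matters most here, because PD-L1+ subjects form one of the two primary populations. Both models needed for a likelihood-ratio test are already fitted, and the SAP gives no reason for treating ORR and OS differently.

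**Working it through.** The documents state no figure for this test, so there is none to reproduce. The check compares the two tests on the same tables and then asks how often the problem could arise.

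**Inputs from the documents**
- Randomized: "with 499 subjects randomized into the Maintenance Phase" (Protocol Synopsis), 1:1.
- PD-L1: "438 samples were available for PD-L1 scoring with the validated assay" and "Less than 15% of the samples were scored as PD-L1 positive" (Protocol Appendix III). 0.15 × 438 = 65.7, so at most about 65 subjects, or 32 to 33 per arm.
- Pooling limit: 0.05 × 499 = 24.95, so about 25 subjects, or 12 to 13 per arm.
- The only avelumab ORR given is 15% (Protocol Section 5.2.3), which is not a maintenance-phase planning rate.

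**Assumed:** response rates by subgroup and arm, since none are given. The tables below illustrate subgroup sizes and are not trial data.

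**Formulas**
- Wald chi-square, two levels: (difference of the two log odds ratios)² ÷ (sum over the four arm-by-level cells of 1/responders + 1/non-responders).
- Likelihood-ratio chi-square: 2 × (log-likelihood with interaction − log-likelihood without).

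**One responder in the sparse cell.** Avelumab 10/33, control 1/32; elsewhere 30/217 in each arm.
- Difference of log odds ratios: ln[(10 × 31)/(23 × 1)] − 0 = 2.60.
- Variance: 1/10 + 1/23 + 1/1 + 1/31 + 2 × (1/30 + 1/187) = 1.253, so SE = 1.12.
- Wald chi-square (2.60/1.12)² = 5.40, p = 0.020. Likelihood-ratio chi-square 8.44, p = 0.004.

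**No responder in that cell.** Avelumab 10/33, control 0/32; elsewhere unchanged.
- The 1/1 term becomes 1/0. Software stops at a finite but meaningless value: estimate 16.4, SE 962 and Wald p = 0.986 with a stopping rule of 1e-8, and p above 0.9999 with a stricter rule.
- Log-likelihoods are −194.61 with the interaction and −201.47 without (common odds ratio 1.39). The likelihood-ratio chi-square is 2 × 6.855 = 13.71, p = 0.0002.

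Removing one control responder makes the heterogeneity stronger, yet the Wald p moves from 0.020 to about 1.

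**At the size of the pooling limit.** Avelumab 7/13, control 0/12; elsewhere 35/237 in each arm. Wald p = 0.9987; likelihood-ratio chi-square 11.00, p = 0.0009.

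**Four-level factors.** With heterogeneity only in the level with the empty cell, joint Wald p is above 0.999 and likelihood-ratio p is 0.010. With heterogeneity in other levels too, they are 0.028 and 0.00009. The joint Wald test loses only the empty level's contribution.

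**Chance that a given cell is empty**, (1 − rate)^n:

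| Assumed ORR | n = 12 | n = 33 |
|---|---|---|
| 3% | 69% | 37% |
| 5% | 54% | 18% |
| 10% | 28% | 3% |
| 15% | 14% | 0.5% |

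**Simulated power at two-sided 5%** (3,000 replicates; 32 and 33 per arm in the subgroup; 14% ORR elsewhere; all rates assumed):

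| Subgroup ORR, control vs avelumab | Wald | Likelihood ratio |
|---|---|---|
| 3% vs 30% | 42% | 88% |
| 1% vs 30% | 19% | 96% |
| 14% vs 1% | 3% | 65% |

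Given an empty cell, the Wald test never rejected; the likelihood-ratio test rejected in 81% to over 99% of replicates. At moderate control rates the gap is small: with 62 subjects in the subgroup, 15% vs 30% gives 23% and 27%, and 10% vs 30% gives 40% and 50%.

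**The case against.** A reader might infer that empty cells are likely across the listed subgroups. The documents do not support that. At 15% a 12-subject arm is empty 14% of the time, and the chance that either arm is empty with 12 and 13 subjects is 1 − (1 − 0.142)(1 − 0.121), about 25%. At PD-L1+ size the figure for one arm is about 0.5%. Only PD-L1+ has a documented size bound; nothing says how many subjects will be MSI-high or aged 75 or over. The category of no metastatic sites belongs to a four-level factor, which can be pooled. What remains is that some features push maintenance-phase responses down. Response must be confirmed and is measured against the Re-Baseline scan. Subjects in CR at Re-Baseline who stay free of disease count as non-responders. The control arm includes subjects on BSC alone.

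A reader might also infer that strong heterogeneity would go unseen. It would not. In the 10/33 vs 0/32 example the subgroup table would show 30% (exact 95% CI 16 to 49%) against 0% (0 to 11%). The within-level CMH chi-square would be (10 − 5.08)²/2.148 = 11.28, p = 0.0008. An SE in the hundreds is also visibly a failed estimate. This stands, although a within-level test does not answer the interaction question.

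Last, the power comparison is not matched for size. With equal subgroup rates of 5 to 15% in both arms, the Wald test rejects 0 to 3.4% of the time and the likelihood-ratio test 2.6 to 8.4%, so part of the gain comes from a more liberal test. That does not explain p-values of about 0.99 and 0.0002 on the same table.

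**Conclusion.** The point holds for the 13 two-level factors when one arm of one level has no responders and the other arm has some. The specified p-value is then about 1 whatever the data show, and the interaction odds ratio and its CI cannot be estimated. For race and number of metastatic sites the loss is partial. If both arms of a level are empty, a Wald p near 1 hides nothing.

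How often this will happen cannot be settled from the documents; it depends on response rates and subgroup sizes that they mostly do not give. The effect is confined to a supportive interaction p-value and its odds ratio, with no multiplicity adjustment. BOR itself is tested only after both OS hypotheses and PFS are rejected, and no confirmatory test, boundary or sample size changes. This is a cheap improvement, not a threat to the trial's conclusions.

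**What to change.** In the Subgroup Analysis paragraph of SAP Section 15.2.2, replace the bracketed Wald Chi-Square test with the Likelihood Ratio test, comparing the two models already fitted, as in Section 15.1.4. Add one sentence: where a subgroup-by-arm cell has no responders, or only responders, report the interaction odds ratio with a Firth-penalised or profile-likelihood CI in place of the Wald interval. A profile-likelihood interval will be open on one side in that case; the Firth estimate stays finite.

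The cost is a wording change and no new models for the test itself. The downside to record is that the likelihood-ratio test is mildly liberal in sparse subgroups, about 7 to 8% at a nominal 5%. Over 15 unadjusted factors that will produce a few more chance findings, which is acceptable for an exploratory test if the report says so.
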